8.4 Administration of Investigational Medicinal Product

IMP will be administered according to the Schedule of Procedures (Appendix A).

The preferred site for administration is the deltoid muscle of the non-dominant upper arm (for example, injection in the left arm if the volunteer uses mainly the right arm) for groups A, B, C and D, unless contraindicated for another reason. For group D1, the site for administration is the vastus lateralis muscles in the quadriceps muscles of the upper legs. In groups with 2mL volume, one injection of 1.0mL each will be given in each deltoid. In groups with 3mL volume, one injection of 1.5mL each will be given in each deltoid for Group D, or three injections of 0.5mL each, will be given in each vastus lateralis for Group D1. In group D1, the administration will be conducted under ultrasound guidance.

Further information on the administration of the IMP is supplied in the SOM.

8.5 Accountability and Disposal of Investigational Medicinal Product

All used vials will be returned to the pharmacy at the end of each vaccination visit. The date, vial allocation number and location of storage of the returned vials will be recorded.

During the study, the IMP accountability forms including dispensing and returning of vials will be kept and monitored.

At the end of the study, the used and unused vials will be handled according to instructions of Sponsor.

Further information on Accountability and Disposal is supplied in the SOM.

8.6 Containment and Transmission of rAAV1-PG9DP Vector

The rAAV1-PG9DP is a replication deficient recombinant AAV-1 vector containing genes of human IgG1-PG9 variable heavy (VH) and variable light (VL) domains and hence does not have the ability to replicate or be transmitted. As part of our testing strategy, the vector product will be tested for replication competent AAV particles. AAV vectors can be handled in Containment Level 1 conditions. AAV is not listed as a human pathogen and although the genetic modification introduces the IgG1-PG9 gene sequences into the AAV vector this does not alter the classification of Containment Class 1.

9.0 ASSESSMENTS

9.1 Safety Assessments

Data on local and systemic reactogenicity will be collected by structured interview and medical examination (i.e., solicited AEs). Data on other (unsolicited) adverse events will be collected with open-ended questions. All data will be recorded on the appropriate source documents and entered into the study database. Volunteers will be given a Memory Aid, which is a tool to assist with collecting reactogenicity data.

Local and systemic reactogenicity events will be assessed by study staff prior to injection and at least 30 minutes and for a total of at least 4 hours post-injection as specified in the Schedule of Procedures (Appendix A). Volunteers will be closely monitored on-site at the clinical facility for symptoms of anaphylaxis.

9.1.1 Local reactogenicity

The presence of local reactogenicity will be assessed at the time points specified in the Schedule of Procedures (Appendix A).

Pain, tenderness, erythema/skin discoloration, swelling/hardening or thickening will be assessed and graded using Appendix B, Adverse Event Severity Assessment Table, as a guideline.

9.1.2 Systemic reactogenicity

The presence of systemic reactogenicity will be assessed at the time points specified in the Schedule of Procedures (Appendix A).

Fever, chills, headache, nausea, vomiting, malaise and myalgia will be assessed and graded using the Appendix B, Adverse Event Severity Assessment Table as a guideline.

9.1.3 Assessment of Lymph Nodes

At injection visit, an assessment of cervical and axillary lymph nodes is performed by study staff prior to injection, and at the first post-injection visit (Day 3). If lymphadenopathy is increased relative to baseline, it will be followed until resolution. For the other study visits, lymph nodes will be assessed at the time points specified in the Schedule of Procedures (Appendix A).

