6.2 Injection Visit

Prior to the injection, study staff will:

- Answer any questions the volunteer may have about the study
- Review the Informed Consent Document with the volunteer
- Review screening safety laboratory data
- Conduct HIV risk assessment
- Conduct HIV testing, HIV test counselling and HIV risk reduction counselling
- Review interim medical history
- Collect concomitant medication information
- Perform a symptom-directed physical examination (refer to Section 7.2)
- Assess cervical and axillary lymph nodes
- Prior to injection, assess local and systemic signs and symptoms (this includes an examination of injection site)
- Collect specimens as indicated in Section 9.1.10
- Perform ECG
- Assign an allocation number to the volunteer according to the instructions specified in the Study Operations Manual (SOM)

Administer the IMP as specified in Section 8.4, Administration of IMP and according to the instructions specified in the SOM.

Observe volunteer closely for at least 30 minutes and then for a total of 4 hours after injection for any acute reactogenicity and symptoms of anaphylaxis.

At the end of each observation period, or if any clinical signs of adverse reactions are observed, study staff will:

- Record vital signs (pulse, respiratory rate, blood pressure and temperature)
- Assess any local and systemic reactogenicity
- Assess any other adverse events

6.3 **Post-Injection Visits**

The volunteer will be asked to return to the clinic on Day 3 (+/- 1 day), Day 7 (+/- 3 days), Day 14 (+/- 3 days), Day 21 (+/- 3 days), Day 28 (+/- 3 days), Day 35 (+/- 3 days), and Day 42 (+/- 3 days) after injection for an assessment by clinic staff. The volunteer will be asked to maintain a Memory Aid from the day of the injection and for the next 7 days. Study staff will review the Memory Aid with the volunteer and determine the severity of the reactions through discussion with the volunteer.

The following procedures will be conducted at these visits:

- Review interim medical history
- Collect concomitant medication information
- Perform a symptom-directed physical examination if any signs or symptoms are present
- Assess cervical and axillary lymph nodes
- Assess local and systemic reactogenicity (Days 3 and 7 only)
- Assess any adverse events
- Collect specimens as indicated in the Schedule of Procedures (Appendix A)
- Perform ECG

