7.2 Medical History and Physical Examination

Medical History

At screening, a comprehensive medical history will be collected including previous vaccinations and reaction to vaccinations, history of STI and contraceptive practices. The Registered General Practitioner of each volunteer will be contacted to obtain medical history relevant to his participation in this trial. At subsequent visits, an interim medical history will be obtained.

Physical Examination

General Physical Examination

A general physical examination includes examination of skin, respiratory, cardiovascular, abdominal, neurological and musculoskeletal systems at the time points indicated in the Schedule of Procedures (Appendix A).

Symptom-Directed Physical Examination

A symptom-directed physical examination includes the examination of skin, respiratory, cardiovascular, abdominal, neurologic and genital systems that are indicated by history or observation. This examination is done at the time points indicated in the Schedule of Procedures (Appendix A).

Measuring Height and Weight

Height and weight are measured at the time points indicated in the Schedule of Procedures (Appendix A).

Assessment of Lymph Nodes

An assessment of cervical and axillary lymph nodes is performed at the time points indicated in the Schedule of Procedures (Appendix A).

Vital Signs

Vital signs including pulse, respiratory rate, blood pressure and temperature are measured and recorded at the time points indicated in the Schedule of Procedures (Appendix A)

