APPENDIX A: SCHEDULE OF PROCEDURES

Study Month		0							1				2		3		4	5	6	9	12 ¹	
Study Day	Screen	0	0	0	3	7	14	21	28	35	42	49	56	70	84	98 ⁵	112	140	168	252	336 ¹	350⁵
Visit Windows (Days)	-42	0	0	0	±1	±3	± 3	± 3	± 3	± 3	± 3	± 3	± 3	± 3	± 7	±3	±7	±7	±7	± 7	±7	±3
VISIT	01	02	02A (30min post)	02B (4hrs post)	02C	02D	03	04	05	06	07	07M	08	08M	09	09M	10	11	12	13	14	14M
INVESTIGATIONAL MEDICINA	AL PRO	DUC	т																			
Investigational Medicinal Product/Placebo		X																				
CONSENT/ASSESSMENTS/	COUNS	ELL	NG		1		-		1	•		-	•					-		T		
Informed Consent	X																					
Screening Assessment	х																					
HIV Risk Assessment		Х																			Х	
HIV Risk Reduction Counselling	Х	X																	Х		Х	
HIV Test Counselling	х	Х																	Х		Х	
Contraception Counselling	X	Х							Х				Х									
Social Impact Assessment																					Х	
CLINICAL SAFETY ASSESS	IENTS																			•		
Comprehensive Medical History	X																					
Interim Medical History		Х			Х	Χ	Χ	Х	Х	Х	Х	Х	Х	Х	Х	Х	Х	Х	Х	Х	Х	Х
Concomitant Medications	X	Х			х	x	х	Х	Х	х	х	Х	Х	X	Х	Х	X	Х	х			X
General Physical Exam	x																				Х	
Symptom Directed Physical Exam		X			х	Х	Х	Х	х	х	x	Х	x	x	Х	х	x	X	х	х		x
Weight	X																				Х	
Height	Х																					
Vital Signs	Х	Х	X	Х					Х				Х		Х						Х	
Cervical & Axillary Lymph Nodes	Х	Х			х	x	x	х	х	х	x	Х	x									

Study Month		0							1				2		3		4	5	6	9	12 ¹	
Study Day	Screen	0	0	0	3	7	14	21	28	35	42	49	56	70	84	98 ⁵	112	140	168	252	336 ¹	350 ⁵
Visit Windows (Days)	-42	0	0	0	±1	± 3	± 3	±3	± 3	±3	± 3	± 3	± 3	± 3	±7	±3	±7	±7	±7	±7	±7	±3
VISIT	01	02	02A (30min post)	02B (4hrs post)	02C	02D	03	04	05				08	08M	09	09M	10	11	12	13	14	14M
Local & Systemic Reactogenicity		x	x	x	x	x																
Adverse Events		Χ	Х	Х	Х	Х	Х	Х	Х	Х	х	Х	Х	Х	Х	Х	Х	Х	Х			Х
Serious Adverse Events and pIMD	x	х	x	x	х	х	х	х	х	Х	x	Х	х	x	х	х	х	Х	х	х	Х	х
Muscle biopsy (group D1 only)															х						х	
CLINICAL LABORATORY TE	STS			•	•								•									
Screening Labs	X																					
Safety Labs	Х	Χ			X ²	Х	Х	Х	Х	Х	х	X^4	Х	X ⁴	Х		Х	Х	Х	Х	Х	
12- lead ECG	Х	Х			Х	Х	Х	Х	Х	Х	Х	Х	Х	Х	Х		Х	Х	Х	Х	Х	
HIV Diagnostics	Х	Х																	X ³		Х	
HLA sample		Х																				
IMMUNOGENICITY ASSAYS						ı 					•		 									
PG9 antibody	X	Х			X	X	Х	Х	Х	Х	x		Х		Х		Х	Х	Х	Х	Х	
Anti-PG9 antibody		Х							Х		х				Х		Х	Х	Х	Х	Х	
Anti-AAV1 and Anti-AAV2 antibodies	x								х		x				Х		x	х	Х	х	Х	

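### The lymph node checks were not adapted when Group D1 moved to thigh injection, so lymphadenopathy is collected on a different basis in D1 than in D and may be under-recorded there

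*Protocol*

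**What the plan says.** Injection site. Section 8.4 of the protocol separates the two groups that receive the same top dose. For Group D, "one injection of 1.5mL each will be given in each deltoid for Group D". For the expansion group, "For group D1, the site for administration is the vastus lateralis muscles in the quadriceps muscles of the upper legs", as three 0.5 mL injections per side.

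Node assessment. Section 9.1.3 says that at the injection visit "an assessment of cervical and axillary lymph nodes is performed by study staff prior to injection" and again at Day 3, and that any increase over baseline is followed until it resolves. Section 7.2 says "An assessment of cervical and axillary lymph nodes is performed at the time points indicated in the Schedule of Procedures". The task lists for the injection visit (Section 6.2) and the post-injection visits (Section 6.3) both carry the line "Assess cervical and axillary lymph nodes". The row in Appendix A is headed "Cervical & Axillary Lymph Nodes". None of these places has a rule or footnote for D1, although Appendix A has D1-only entries for the biopsy and for its follow-up visits. Inguinal nodes are mentioned nowhere.

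Other ways to detect a node. Section 7.2 says: "A symptom-directed physical examination includes the examination of skin, respiratory, cardiovascular, abdominal, neurologic and genital systems that are indicated by history or observation". Section 9.1 adds: "Data on other (unsolicited) adverse events will be collected with open-ended questions". Section 9.1.5 collects adverse events through Day 168 and serious adverse events throughout.

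**The concern.** The node check fits an arm injection, where the neck and armpit are the regions to examine. Under the version 6.0 amendment D1 moved to the quadriceps. The dosing and biopsy text was revised and the safety biopsy in Section 9.1.8 was generalised from the deltoid to whichever muscle was injected, but the summary of changes lists no revision of the node text. This looks like an oversight rather than a decision.

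At stake is how evenly one safety item is ascertained. Groups A to D have the nodes draining the injected muscle palpated before injection and repeatedly afterwards. For D1 the equivalent nodes depend on the volunteer or clinician noticing something. Section 2.4 reports dose-related inflammation at the injection site in mice, and Section 2.7 treats an immune response to the expressed protein as a main risk, so a regional node reaction is a reasonable thing to look for at the top dose. If D and D1 lymphadenopathy rates are tabulated next to each other, they will not have been collected in the same way.

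**Working it through.** No figure in the protocol depends on this point, so the main check sets the passages side by side.

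1. Site against region examined. Groups A to D: deltoid; cervical and axillary nodes examined. Group D1: vastus lateralis; cervical and axillary nodes examined. The protocol does not name the draining nodes. That the arm drains to the axilla and the thigh to the groin is general anatomy and is taken as given.

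2. Baseline. The general physical examination at screening (Section 7.2) covers skin, respiratory, cardiovascular, abdominal, neurological and musculoskeletal systems. It schedules no groin or lymph node check, so it supplies no inguinal baseline.

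3. Visits affected, from the Appendix A row: Screening and Days 0, 3, 7, 14, 21, 28, 35, 42, 49 and 56, which makes 11.

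4. Volunteers affected, from Table 5.0-1. D1 has 4 active + 1 placebo = 5. Top-dose active: 3 (D) + 4 (D1) = 7, and 4/7 = 57%. All active on the path through D1: 3 + 3 + 3 + 3 + 4 = 16, and 4/16 = 25%. These are headcounts, not an effect size.

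5. What the groups can show in any case. The exact two-sided 95% upper limit for 0 events in n is 1 − 0.025^(1/n). For n = 3 this gives 70.8%, which reproduces Section 14.2. For n = 4 it gives 60.2%. An empty node finding in D1 would say little even with a complete examination.

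6. Possible size of under-recording. The protocol gives neither a lymphadenopathy rate nor a capture rate, so both are assumed here. Let p be the true rate in both groups, with full capture in D, and let c be the fraction captured in D1. The expected recorded rate in D1 is p × c, below p whenever c < 1. The chance of recording at least one case is 1 − (1 − p)^3 in D and 1 − (1 − pc)^4 in D1:

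| p | D | D1, c = 0 | c = 0.25 | c = 0.5 | c = 0.75 | c = 1 |
|---|---|---|---|---|---|---|
| 0.1 | 0.271 | 0.000 | 0.096 | 0.185 | 0.268 | 0.344 |
| 0.3 | 0.657 | 0.000 | 0.268 | 0.478 | 0.639 | 0.760 |
| 0.5 | 0.875 | 0.000 | 0.414 | 0.684 | 0.847 | 0.938 |

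Setting the two chances equal gives c = [1 − (1 − p)^(3/4)]/p, which is 0.76, 0.78 and 0.81 for the three rates. Because D1 has one more active recipient, it is less likely than D to record a case only when capture falls below about three quarters to four fifths.

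**The case against.** A reader might infer that regional lymphadenopathy cannot be seen in D1 at all. The documents do not support that. Interim history and symptom-directed examination are scheduled at nearly every visit after injection, the latter can extend to the skin and genital systems, adverse events are asked about openly through Day 168, and serious and potentially immune-mediated events are collected throughout. A painful or noticed groin node has a route into the data. These routes are weaker than scheduled palpation: Section 6.3 makes the examination conditional on signs or symptoms, lymph nodes are not among the systems listed, and none of the routes provides a baseline.

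A reader might also infer that D1 will look falsely cleaner than D. That would require node reactions to occur, to occur in D at a similar rate, and to be missed often enough in D1. The documents give no rate for any of these.

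The consequences are also limited, and this part of the objection stands. Lymphadenopathy is on neither solicited list (Sections 9.1.1 and 9.1.2). An asymptomatic node would probably be Grade 1 on the general scale, outside the moderate-or-greater endpoints of Section 4.1.1 and below the pausing criteria in Section 17.4 that are set by severity grade. Section 14.2 bases the safety analysis on within-group description, and Section 2.5.1 gives gene expression as the reason for the D/D1 contrast. No planned Safety Review Board review or dose escalation follows D1. Local tissue is examined more closely in D1, through biopsies at 3 and 12 months, although these sample muscle rather than nodes.

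Finally, the last summary of changes says that enrolment is complete, so a pre-injection inguinal baseline may no longer be obtainable.

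**Conclusion.** The point holds as a mismatch between the injection site and the scheduled node assessment. Following the protocol as written, all 11 node checks in D1 omit the region that drains the injected muscle, and the comparison with baseline in Section 9.1.3 has nothing to work from there. Asymptomatic inguinal enlargement may go unrecorded, so lymphadenopathy is ascertained on a different basis in 4 of the 7 top-dose active recipients than in the other 3.

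The likely direction is under-recording in D1. Its size cannot be stated, because it depends on an unknown rate and an unknown capture fraction, and with 3 and 4 active recipients chance would dominate any observed difference. The effect is confined to this one item. The documents do not support a claim that the primary safety endpoints or the overall tolerability of D1 are biased. The conclusion assumes ordinary lymphatic anatomy and that no D1-specific instruction exists in the Study Operations Manual, which is not available here.

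**What to change.** Reconcile Sections 6.2, 6.3, 7.2 and 9.1.3 and the Appendix A row with the D1 injection site: for D1, add inguinal nodes at the node visits already scheduled, including the pre-injection baseline, and keep the cervical and axillary checks so that those regions remain comparable across groups. The cost is a wording change, a line on the D1 source form and a brief added palpation, with no new visit.

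Where D1 baselines have already passed, the remaining step is in the reporting: state that inguinal nodes were not systematically examined in D1 and that lymphadenopathy rates are not comparable between D and D1. That costs a footnote in the safety tables.

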9.1.4 Vital Signs

At injection visit, vital signs (pulse, respiratory rate, blood pressure and temperature) will be measured by study staff prior to injection and at least 30 minutes and 4 hours post-injection. For the other study visits vital signs will be assessed at the time points specified in the Schedule of Procedures (Appendix A).

9.1.5 Other Adverse Events

Other adverse events (AEs) will be collected through Day 168. Serious Adverse Events (SAEs) will be collected throughout the entire study period. Open ended

questions will be asked at time points according to the Schedule of Procedures (Appendix A). All adverse events will be graded using Appendix B, Adverse Event Severity Assessment Table, as a guideline and will be assessed for causality to the IMP. For more information regarding adverse events refer to Section 10.0, Adverse Events.

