SAFETY MONITORING AND STATISTICAL CONSIDERATIONS	All clinical trial data collected, identified only by a study identification number, will be entered into a database. Safety will be continually monitored by the Investigators, the Sponsor's Medical Monitor and a Protocol Safety Review Team (PSRT); detailed stopping criteria are pre- defined. All safety data will be reviewed by an independent Safety Review Board (SRB). Ad-hoc safety review may be specifically requested by the Sponsor, the Principal Investigators, Ethics Committees, Regulatory Authorities, or by the SRB. At the end of the study, a full analysis will be prepared according to a pre-specified statistical analysis plan. All clinical and routine laboratory data will be included in the safety analysis. Antibody and immunogenicity analyses will be performed according to a predefined analysis plan for all volunteers who received IMP or placebo.

TABLE OF CONTENTS

ABB	REVIATIONS	11
CON	TACT INFORMATION	12
1.0	SIGNATURE PAGE	14
2.0	INTRODUCTION AND BACKGROUND INFORMATION	
2. 2.3 2.4 2.5	Experience with recombinant AAV vectors	17 17 19 20 21 21 22 22 23
3.2	Secondary Objectives	23
4.0	STUDY ENDPOINTS	24
	Study Endpoints	24
5.0	STUDY DESIGN	24
5.1 5.2 5.3 5.4 5.5	Study Population Inclusion Criteria Exclusion Criteria	27 27 27
6.0	STUDY VISITS	30
6.1 6.2 6.3 6.4 6.5 6.6	Injection Visit Post-Injection Visits Additional Follow-up Visits Unscheduled Visits	31 32 32 32
7.0	STUDY PROCEDURES	33
7.1 7.2 7.3 7.4 7.4 7.5 7.6	Medical History and Physical Examination HIV Testing and HIV Test Counselling HIV Risk Reduction Counselling Contraception Counselling Specimens.	33 34 34 34 34

 7.7 Randomization and Blinding 7.8 Unblinding Procedure for Individual Volunteers 7.9 Referral to Long Term Follow-Up Study 	

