Routine clinical safety laboratory tests – complete blood count, electrolytes, and renal and liver function – will be assessed at every scheduled visit. If an immune response is generated to the expressed foreign protein, potential clinical disease could consist of an inflammatory response either locally in the muscle, or systemically as immune-mediated disease: for example immune hepatitis, nephritis, vasculitis or arthritis. Volunteers will be monitored carefully at each scheduled visit for evidence of immune-mediated diseases with history and physical examination as well as renal and liver function tests, C-reactive protein as a general screen for inflammation, creatine kinase as a general screen for muscle inflammation, and urinalysis to look for evidence of immune-mediated nephritis. The Medical Advisory Panel (see Section 7.4) will evaluate all potential immune-mediated diseases and advise on drug treatment if necessary. A short course of oral corticosteroid will be the initial treatment but additional or alternative medications will be considered depending on the type of disease and volunteer characteristics. See Appendix C for detailed treatment plan.

Because one preclinical study found cases of mild cardiac fibrosis in mice, cardiac troponin I will be assessed at baseline and each scheduled visit to look for evidence of cardiac inflammation and electrocardiogram will be evaluated baseline and at each scheduled visit for evidence of clinically significant cardiac disease.

Anti-PG9 levels will also be evaluated. An elevated anti-PG9 level or a drop in neutralization titre may indicate an immune response to the expressed protein. Alone these findings will not represent adverse events but may be needed to interpret causality of clinical events.

Because this delivery system is designed to produce long-term protein expression, evaluation of long-term safety is an important component of product development. After the trial-specified safety monitoring for 48 weeks after a single administration, volunteers will be asked to enrol in a long-term follow-up protocol to monitor safety for a total of at least 5 years after IMP administration.

See the rAAV1-PG9DP Investigator Brochure for a full description of the preclinical and clinical immunogenicity and safety profile of this candidate product, including potential on-target and off-target effects.

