4.0 STUDY ENDPOINTS

4.1 Study Endpoints

4.1.1 **Primary Endpoints**

Safety and tolerability:

- **1.** Proportion of volunteers with moderate or greater reactogenicity (i.e., solicited adverse events) during a 7 day follow-up period after each injection
- 2. Proportion of volunteers with moderate or greater adverse events (i.e., unsolicited adverse events), including safety laboratory (biochemical, haematological) parameters, from the day of injection up to 168 days post injection
- 3. Proportion of volunteers with serious adverse events (SAEs) related to the IMP throughout the study period
- Proportion of volunteers in each group with potential Immune Mediated Diseases (pIMDs), defined as adverse events potentially caused by antigen-antibody complexes or immune responses directed to cells producing the transgene

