9.1.9 Concomitant Medications

Concomitant receipt of other IMPs is prohibited during the study.

All medication ongoing at study entry will be documented. (See DCF instructions on DCC website)

During the study, information regarding concomitant medications and reasons for their use will be solicited from the study volunteers until six months after the injection. Ongoing concomitant medications will be recorded until end of study.

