17.4 Criteria for Pausing the Study

Enrolments and injections will be paused, a formal study halt will be submitted to the MHRA as a substantial amendment, and a safety review conducted by the SRB for any of the following criteria:

- 1. One volunteer develops a Grade 3 or 4 adverse event that is judged to be possibly, probably or definitely related to IMP;
- 2. Grade 2 adverse events that persists for more than 7 days that is possibly, probably or definitely related to the IMP;
- 3. One volunteer experiences a serious adverse event that is probably or definitely related to the IMP, or two or more subjects experience similar serious adverse events which are possibly related to the IMP;
- 4. There is a volunteer death assessed as possibly, probably or definitely related to the IMP;
- 5. One volunteer shows evidence of disease that might be due to immune complexes and is judged to be possibly, probably or definitely related to IMP, such as acute arthritis, severe generalized rash, or glomerulonephritis;
- 6. A 5-fold increase in ALT within 10 weeks after IMP administration which is not responsive to oral corticosteroids and is judged to be possibly, probably or definitely related to IMP.

The Sponsor will request a review by the SRB, (or the SRB chair if other SRB members cannot be convened), to be held within 2 business days of the Sponsor learning of the

event. The individual volunteer(s)/or study may be unblinded at the discretion of the SRB.

Following this review, the SRB will make a recommendation regarding the continuation or suspension of the vaccinations or the trial and communicate this decision immediately to the Sponsor. If the SRB decision is to restart enrolments and injections, then a further substantial amendment will be submitted to the MHRA including all appropriate safety data and justification to restart. The Sponsor then will inform the Principal Investigator of the MHRA decision.

Additional *ad hoc* review may be specifically requested by the Sponsor, the Principal Investigator(s) or by the SRB.

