HIV neutralization		X							Х		Х				Х		Х	Х	Х	Х	Х	
AAV1 distribution (blood)		Х			Х	Х	Х	Х	Х						Х							
AAV1-specific T cell responses		x									x				Х						Х	
PBMC collection		Х									Х				Х						Х	

¹Early Termination (ET): Procedures to be performed at ET are the same as last visit procedures ²See Section 9.1.10 for tests not included at Day 3 ³If HIV infected, conduct ET visit, see SOM for details

⁴ Cardiac troponin I only

⁵ Muscle biopsy safety assessment follow-up visit for Group D1 volunteers only. This visit may be conducted by telephone or as a clinic visit. If visit is conducted by phone then symptom-directed physical exam is not required. Study clinician may request the volunteer to return to the clinic for assessment if clinically indicated.

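### Non-serious, non-pIMD adverse events and newly started medications go uncollected after Day 168 / six months, although visits run to Day 336 and two pause criteria rely on adverse events without a time limit

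*Protocol*

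**What the plan says.** - **Collection windows.** Section 9.1.5 says "Other adverse events (AEs) will be collected through Day 168" and "Serious Adverse Events (SAEs) will be collected throughout the entire study period". Section 9.1.6 collects pIMDs for the whole study through the SAE process. Primary endpoint 2 (4.1) has the matching window, "from the day of injection up to 168 days post injection".
- **Medications.** Section 9.1.9 solicits medications "until six months after the injection". Those already ongoing are recorded to the end of the study.
- **Visits.** Appendix A marks interim history, a physical examination (symptom-directed at Day 252, general at Day 336), safety labs and ECG at both late visits. The Adverse Events and Concomitant Medications rows are blank there. Both are marked again at Day 350, which footnote 5 describes as "Muscle biopsy safety assessment follow-up visit for Group D1 volunteers only".
- **Pause rules.** In 17.4, criterion 1 is one related Grade 3 or 4 adverse event. Criterion 2 is "Grade 2 adverse events that persists for more than 7 days that is possibly, probably or definitely related to the IMP". Neither has a time limit, whereas criterion 6 is limited to 10 weeks.
- **pIMD reporting.** Section 10.5 tells staff to hold isolated nonspecific symptoms as adverse events until a pIMD diagnosis can be defended.
- **Stated monitoring.** Section 2.7 refers to follow-up "After the trial-specified safety monitoring for 48 weeks after a single administration". The Synopsis says "All clinical and routine laboratory data will be included in the safety analysis".

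**The concern.** Section 2.1 hypothesises PG9 expression for at least 12 months, and the primary objective is safety. Section 10.1 counts an abnormal laboratory finding as an adverse event, and 9.1.7 says the ECGs look for cardiac adverse events. At Days 252 and 336 the trial makes these measurements, but 9.1.5 gives a new non-serious finding no place to be recorded as an adverse event.

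Three consequences follow:

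1. Pause criteria 1 and 2 are written for the whole injection period, but part of their input ends at Day 168 for each volunteer while later groups may still be dosed.
2. The holding category that 10.5 uses for undiagnosed immune symptoms closes at Day 168. That weakens primary endpoint 4 (pIMDs), which has no such limit.
3. PG9 and anti-PG9 are measured to Day 336, but a corticosteroid or other immunosuppressant newly started after six months is not asked about.

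**Working it through.** **Share of follow-up affected.** The last main visit is Day 336, which equals the 48 weeks in 2.7 (48 × 7 = 336). Uncovered: (336 − 168) / 336 = 50%.

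**Calendar inputs.** The first three injections in Groups A to D are 7 days apart (5.0), so the last two of four can be given on day 14 of the group. SRB reviews follow 42, 42, 56 and 56 days after the last injection in A, B, C and D (17.2.1). Day 0 is the first Group A injection. Let g be the days lost to review and recruitment at each of the four steps. The protocol does not give g.

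Fastest case, g = 0:

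| Group | First injection | Last injection | Day 168 falls on |
|---|---|---|---|
| A | 0 | 14 | 168–182 |
| B | 14 + 42 = 56 | 70 | 224–238 |
| C | 70 + 42 = 112 | 126 | 280–294 |
| D (or C1) | 126 + 56 = 182 | 196 (D) | 350–364 (D) |
| D1 | 196 + 56 = 252 | – | – |

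- When D opens (day 182), all 4 Group A volunteers have reached Day 168, the last two on that very day. With the ±7-day window their Day 168 visit could fall as late as day 189.
- When D1 opens (day 252), all 8 volunteers in A and B have passed Day 168. Groups C and D are still covered.

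**Effect of delay.** D opens on 182 + 3g and D1 on 252 + 4g.

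- All of B is past Day 168 when D opens if 238 + g ≤ 182 + 3g, that is g ≥ 28.
- All of C is past it when D1 opens if 294 + 2g ≤ 252 + 4g, that is g ≥ 21.

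The only stated pace is about 13 months to enrol (5.1), roughly 13 × 30.44 = 396 days. The 252-day minimum is compatible with that figure but cannot reproduce it. Assume the 13 months run to the D1 opening and the delay is equal at each step. Then g ≈ 35.75, D opens on about day 289 and D1 on about day 395. Groups A and B (8 of 12) are past Day 168 at the D opening, and A, B and C (12 of 16) at the D1 opening.

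**What the late visits could add before dosing.** At g = 0, Group A's Day 252 visits fall on days 252–266, on or after the D1 opening. At the 13-month pace those visits precede the D opening. Group A's Day 336 visits (days 336–350) and Group B's Day 252 visits (about days 344–358) precede the D1 opening.

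**Which channels stay open after Day 168:**

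| Event after Day 168 | Collected? | Route to a pause or to the SRB |
|---|---|---|
| SAE, death | Yes | Criteria 3 and 4; criterion 1 if related and Grade 3–4 |
| pIMD | Yes | Criterion 5 if it fits; criterion 1 if related and Grade 3–4 |
| ECG, troponin | Yes | Summaries at planned reviews (17.2.1), escalation criteria (17.2.2) |
| Event with onset before Day 168 | Followed (10.6) | Already recorded as an adverse event |
| New non-serious, non-pIMD Grade 2–4 event | No | None specified for criteria 1 and 2 |

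**The case against.** The cut-off is deliberate. Day 168 appears in the Synopsis, 4.1, 9.1.5 and Appendix A, and 9.1.9 stops at the same six months. Nothing in the plan requires endpoint 2 to run longer. That stands, but an endpoint window need not limit what is collected.

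A reader might infer that the pause rules cannot see any late Grade 2–4 event. The documents do not support this: the pIMD list in 10.5 covers many of the feared late toxicities, including myopathy, autoimmune hepatitis, glomerulonephritis and myocarditis. Criteria 3 to 5 stay fed, and criterion 6 expires long before Day 168. The PSRT also reviews clinical safety data weekly until 6 weeks after the last injection (17.1), and ad hoc reviews can be requested.

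A reader might also see a contradiction with the Synopsis or 2.7. There is none: late laboratory values still enter the safety analysis, and 48 weeks of monitoring take place. What is missing is their recording as adverse events.

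Nor does Day 350 bias primary endpoint 2, which ends at Day 168. It is a follow-up contact after a biopsy that only D1 has. The mark still disagrees with the wording of 9.1.5.

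Two further points stand. On the fastest calendar only the groups at one-thirtieth (A) and one-third (B) of the D1 dose are past Day 168 when D1 opens. And the final summary of changes reports enrolment complete, so in this version the pause-rule argument concerns the design as written. For medications, the gap is only newly started ones; treatment of a product-related immune disease would come to notice through the pIMD report and the Medical Advisory Panel.

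**Conclusion.** The point holds in limited form. For half of main follow-up, new non-serious, non-pIMD adverse events and newly started medications are not collected, although the visits are held. Criteria 1 and 2 in 17.4 have no time limit but lose that part of their input for volunteers past Day 168. This affects essentially all of Group A at the earliest D opening, all of A and B at the earliest D1 opening, and 12 of 16 earlier volunteers at the D1 opening if enrolment runs at the stated 13 months.

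The calendar rests on the protocol's minimum intervals and on an assumed equal delay per step. The recording gap does not depend on the calendar, but its practical weight depends on how many volunteers still had late visits ahead, which the document does not say. No primary endpoint is mis-specified. Sections 9.1.5, 9.1.9, 10.5, 17.4 and the Day 350 mark need reconciling, as a low-cost improvement in safety ascertainment.

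**What to change.** In Appendix A, mark Adverse Events and Concomitant Medications at Days 252 and 336. Restricting late adverse events to Grade 2 or higher is acceptable for criteria 1 and 2. If that limit is used, state how lower-grade nonspecific symptoms under 10.5 are to be held. Change 9.1.5 and 9.1.9 so that collection runs to the end of the study, which also covers unscheduled visits and agrees with the Day 350 mark. Leave primary endpoint 2 at 168 days, and add the same proportion through Day 336 as a descriptive summary.

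The cost is two further entries per volunteer at visits that already include history, examination, laboratory tests and ECG, plus some unrelated background events to record and report. On the fastest calendar the added late visits would inform little before D1 opens; at the planned pace they would inform the decisions to open both D and D1.
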